9. EFFECTIVENESS ANALYSES

Effectiveness will be assessed using the ITT Population with subject eyes included in the treatment arm in which they were randomized. Primary and secondary effectiveness endpoints will also be assessed using the PP Population. Data will be presented and analyzed by treatment group and eye. Observed case data will be used; no imputation will be performed for effectiveness data.

9.1. Primary Effectiveness

The change from baseline to each post-baseline visit in distance logMAR VA will be summarized descriptively by treatment group and eye, using letters read as the unit of analysis. Actual values will also be summarized at each visit by treatment group and eye.

The number and percentage of subjects where there is no more than a 5-logMAR letters read loss from baseline (change from baseline in number of letters read ≥ -5) will be summarized at each post-baseline visit by treatment group and eye.

Summaries will be completed for both the ITT and PP populations.

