Secondary effectiveness endpoints:	
Secondary effectiveness endpoints will include distance VA; symptoms/complaints and subjective assessments; lens wettability, centration, and movement; and lens deposits at each post-baseline visit and the satisfaction survey (modified Visual Functioning Questionnaire) at the Screening and Exit Visits.
			
Safety endpoints:	
The primary safety endpoint will be the proportion of eyes with any slit lamp findings (including corneal edema [epithelial, stromal], corneal infiltrates, corneal vascularization, corneal staining, palpebral conjunctival injection, and limbal injection) Grade >2 at any follow-up visit between the test and control lenses.
 
Secondary safety endpoints will include adverse reactions (serious and incidental), adverse device effects, pinhole VA (for eyes with a 2-line decrease in BCDVA or worse from baseline), conjunctival hyperemia as measured by the Cornea and Contact Lens Research Unit grading scale, keratometry, slit lamp biomicroscopy, spherocylindrical refraction, BCDVA, corneal fluorescein staining, lens discontinuation rates at any follow-up visit, and use of unpreserved lubricant eyedrops or artificial tears during the study.
			
Statistics:	
All analyses will be descriptive in nature. A full declaration of planned statistical analyses will be documented in a formal Statistical Analysis Plan.
			
Sample size:	
The sample size of approximately 80 subjects (160 eyes) is considered sufficient for evaluation of the clinical performance of the test and control lenses. The sample size was not based on statistical power considerations. A dropout rate of approximately 20% is expected;
			

	thus, approximately 60 subjects (120 eyes) are targeted to be described in this study.
--	--

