4. STUDY OBJECTIVE

The objective of this clinical study is to provide clinical performance data comparing the test lens (Deseyne [vifilcon C] daily disposable soft contact lens) to a control lens (1-Day Acuvue Moist [etafilcon A] daily disposable soft contact lens) in the same indication for use (single use prior to removal followed by a fresh lens upon the next lens wear exposure).

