7.2. Covariates and Subgroups

7.2.1. Planned Covariates

Planned covariates include baseline values for the given assessment.

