7.3.5. Analysis Software

Data manipulation, tabulation of descriptive statistics, calculation of inferential statistics, and graphical representations will be performed using SAS (release 9.4 or higher) for Windows.

[figure not shown]

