7.4. Planned Study Analyses

7.4.1. Statistical Summaries: Descriptive and Inferential

Safety and effectiveness endpoint results will be presented by treatment group (Deseyne [vifilcon C] and 1-Day Acuvue Moist [etafilcon A]).

All p-values will be rounded to and displayed in four decimals. If a p-value less than 0.0001 occurs, it will be shown in tables as <0.0001. The p-values for the analysis of effectiveness endpoints will be considered descriptive.

Descriptive summaries of variables will be provided where appropriate. For continuous variables, the number of non-missing values (n), mean, standard deviation, median, confidence intervals (CIs), minimum, and maximum will be tabulated by treatment group. Means, medians, and CIs will be presented with 1 more decimal place than the recorded raw data. Standard deviations will be presented with 2 more decimal places than the recorded raw data. Minima and maxima will be presented with the same number of decimal places as the recorded raw data. Values with magnitude <1 will be presented with a leading zero to the left of the decimal (e.g., 0.123).

Categorical data will be summarized using frequencies, percentages, and CIs. Percentages will be presented with 1 decimal place. Percentages may not be presented when the count is 0. Unless otherwise specified, the denominator for percentages will be the number of non-missing values within the group being presented.

All study-related data collected will be presented in listings. Study-related data not subject to analysis according to this plan will not appear in any tables or graphs but will be included in the data listings.

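### The objective is to compare two lenses, but the SAP plans only within-lens summaries; a pre-specified, adjusted test-minus-control estimate with a CI should be added, and ADEs tabulated by lens

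*SAP*

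**What the plan says.** SAP section 4 gives the objective as "to provide clinical performance data comparing the test lens" with the control lens, and SAP 5.1 describes a randomized, active-controlled design for that comparison. The protocol Synopsis (Statistics) says "All analyses will be descriptive in nature". The Synopsis (Sample size) and SAP 6 say that the size does not rest on power.

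On the primary analysis, SAP 9.1 states: "The change from baseline to each post-baseline visit in distance logMAR VA will be summarized descriptively by treatment group and eye". The endpoint of no more than a 5-letter loss is handled the same way, as counts and percentages. SAP 9.2 follows the same pattern for the secondary endpoints.

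SAP 7.4.1 does plan intervals. For continuous variables, "confidence intervals (CIs), minimum, and maximum will be tabulated by treatment group"; and "Categorical data will be summarized using frequencies, percentages, and CIs". It states no confidence level or method.

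Three pieces of text point to an analysis that is nowhere specified:
- SAP 7.2.1: "Planned covariates include baseline values for the given assessment".
- SAP 7.4.1: "The p-values for the analysis of effectiveness endpoints will be considered descriptive".
- SAP 7.3.5, among the uses of the software: "calculation of inferential statistics".

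SAP 5.3 stratifies randomization by site.

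On safety, SAP 4.1.4 names ADEs as a secondary safety endpoint. The opening of SAP section 10 has safety data tabulated by treatment group. SAP 10.1 says that ADEs are not summarized and only listed (Listing 16.2.7.2).

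**The concern.** A comparative objective is normally answered by an estimate of the difference and its uncertainty. Here the reader gets two columns of summaries, each with its own interval, and must construct the contrast. The covariate and the stratification factor that would sharpen or balance that contrast are named but not used. The p-value text suggests that a comparison may have been intended, but no section names a test or model that would produce one.

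If the adjusted estimate is wanted later, for a report or a regulatory question, its model and interval method would be chosen after the data of an open-label study are known.

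For ADEs, a reader who wants device-related events by lens must count them from a listing. The planned TEAE tables (14.3.1.1 to 14.3.1.4) do not separate events by relation to the device.

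**Working it through.** **Is a between-lens estimate planned anywhere?** SAP 7.4.1, 9.1, 9.2 and 10.3 and the table list in 12.1 name summaries by lens, eye and visit. None names a difference, ratio, model or test. Baseline enters only by subtraction in the change score, and site enters nowhere.

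**What can be derived from the planned tables?** They give n, mean, SD and counts by lens, eye and visit. The unadjusted per-eye difference and its interval follow by arithmetic. An estimate adjusted for baseline and site does not, because it needs subject-level data.

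**Sample sizes.** The 2:1 split reproduces: 80 x 2/3 = 53.3 and 80/3 = 26.7, against 53 and 27 in SAP 5.2. The target of 60 does not follow from 20% dropout: 80 x 0.80 = 64, and 60 of 80 is a 25% loss. This does not affect the present point; both 64 (43 v 21) and 60 (40 v 20) are shown below.

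**Precision of the direct estimate.** Half-width of the 95% CI = SD x t(0.975; n1 + n2 - 2) x sqrt(1/n1 + 1/n2), with one eye and therefore one value per subject. The documents give no SD of change, so 3 to 7 letters is an assumption.

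| Subjects | Multiplier of SD | SD 3 | SD 5 | SD 7 |
|---|---|---|---|---|
| 53 v 27 | 0.471 | 1.4 | 2.4 | 3.3 |
| 43 v 21 | 0.532 | 1.6 | 2.7 | 3.7 |
| 40 v 20 | 0.548 | 1.6 | 2.7 | 3.8 |

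For scale, the second primary endpoint uses a 5-letter limit.

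**Effect of baseline adjustment.** Relative to the change score, the ANCOVA half-width is multiplied by sqrt((1 - r^2)/(1 + k^2 - 2rk)). Here r is the correlation of baseline and follow-up, and k is the baseline SD divided by the follow-up SD. Both are assumed.

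| k | r = 0.3 | r = 0.5 | r = 0.7 |
|---|---|---|---|
| 0.7 | 0.92 | 0.97 | 1.00 |
| 0.9 | 0.85 | 0.91 | 0.96 |
| 1.0 | 0.81 | 0.87 | 0.92 |
| 1.3 | 0.69 | 0.73 | 0.77 |

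The 50-letter entry floor (inclusion criterion 4) makes k below 1 plausible, which is where the gain is smallest. Simulation at 40 v 20 with baseline and five balanced sites (1,500 trials per setting) gave factors of 0.70 to 1.01. It assumed no site effect, so it shows the cost of fitting site and not any benefit.

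**Binary endpoint.** With assumed counts of 38/40 v 19/20, the difference is 0.0 points with a Newcombe 95% CI of -12.2 to +19.0. With five equal sites, 40 v 20 is 40/5 = 8 test and 20/5 = 4 control subjects per site, so site strata may be sparse.

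**ADEs.** With 2:1 allocation, one subject with an ADE is 1/53 = 1.9% on test and 1/27 = 3.7% on control. Raw counts from a listing need denominators.

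**The case against.** The strongest defence is that the study is openly descriptive and unpowered. Data comparing two lenses can be supplied by side-by-side summaries, and nothing obliges the SAP to estimate a contrast. That stands: a reader might infer that the SAP contradicts its objective or the protocol, and it does not. Nor does a descriptive design need a hypothesis test, margin or success criterion.

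A reader might also infer that the whole comparison is left to be chosen after the data are seen. That goes too far. Endpoint, baseline, eyes, visits, populations and the observed-case rule are fixed, so the unadjusted difference is determined. Only the adjustment and the interval method stay open.

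It is also tempting to measure the harm by overlap of the two within-lens intervals. At 40 v 20, two 95% CIs separate only at 0.788 SD, against a direct half-width of 0.548 SD, a ratio of 1.44. But the SAP nowhere says that overlap will be used to judge a difference, so this is the cost of a misreading and not of the plan.

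The unattached p-value, covariate and inferential wording may be leftover text. Deleting it would be an editorial fix and does not by itself show that ANCOVA is needed.

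On ADEs, 10.1 can be read as a deliberate exception to the general sentence in section 10. TEAEs, including serious ones and those leading to withdrawal or lens discontinuation, are tabulated by lens, so the information is not lost. What is missing is a by-lens display of events related to the device.

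**Conclusion.** The point holds as an improvement within a declared descriptive design. The study asks how the test lens performs against the control lens, and the SAP stops one step short of the estimate that answers this. The omission leaves the baseline- and site-adjusted difference and its interval method unspecified; it does not lose data.

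The interval would be informative at the planned size: a half-width of about 1.4 to 3.8 letters per eye, on an assumed SD of change of 3 to 7 letters, equal in both arms. The case does not rest on a gain in precision. The adjustment factor runs from about 0.69 to 1.01 over the assumed SD ratios and correlations, so the gain may be nil. The reason to adjust is to use the declared covariate and the stratification factor in a way fixed beforehand.

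The ADE item is separate and adds no weight to the main point. It stands because a named endpoint has no table, and the general rule in section 10 and the sentence in 10.1 should be reconciled.

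**What to change.** 1. **SAP 9.1, letters read.** Keep the by-eye summaries and add: *For the ITT and PP populations, the test-minus-control difference in change in letters read will be estimated by eye at each post-baseline visit, with a 95% CI, from an ANCOVA with lens group, baseline letters and site, on observed cases.* State whether the Dispensing Visit counts as post-baseline, since 7.6 takes the Screening BCDVA as baseline and lens VA is also measured at dispensing.
2. **SAP 9.1, no more than a 5-letter loss.** For the same populations, add the difference in proportions by eye and visit with a score-type 95% CI: Miettinen-Nurminen stratified by site, or unstratified Newcombe if site cells are too sparse. State the rule for choosing in advance.
3. **SAP 7.4.1.** State that these intervals are descriptive, with no test and no multiplicity adjustment (consistent with 7.5). Delete the p-value text or align it, and give the level and method of the within-lens CIs.
4. **SAP 10.1 and 12.1 (separate item).** Add a table of ADEs by SOC, PT and lens group in the safety population, with denominators, and keep the listing.

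Cost: SAP wording, one ANCOVA per eye, visit and population, difference columns in Tables 14.2.1.x and 14.2.2.x, and one new table. No new data are needed. The downside is 2 eyes x 4 visits x 2 populations = 16 further unadjusted intervals per endpoint (20 if dispensing counts), modest programming and validation, and intervals that show openly how limited the precision is.

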9.2. Secondary Effectiveness

Secondary effectiveness endpoints are indicated in Section 4.1.

All effectiveness data for continuous endpoints will be summarized descriptively at each visit, showing actual values and change from baseline values by treatment group. For effectiveness endpoints that assess each eye separately, summaries will be created for each eye. Categorical effectiveness endpoints will be summarized using counts and percentages by treatment group and eye, where applicable.

Summaries will be completed for both the ITT and PP populations.

Responses to the satisfaction survey (modified VFQ) will not be tabulated but will be listed.

10. SAFETY ANALYSES

All safety analyses will be conducted using the SP. All safety analyses will be completed using the actual treatment a subject received. Observed case data will be used; no imputation will be performed for missing safety data except for the limited situations described in Section 7.3.2. Safety data will be tabulated and summarized descriptively by treatment group. Each eye will be treated independently for safety purposes.

All safety data will be presented in by-subject listings.

10.1. Adverse Events and Adverse Device Events

AEs will be coded using MedDRA, Version 26.1.

Treatment-emergent adverse events (TEAEs) are defined as any AE that begins or worsens after lens dispensing. If the onset of an AE is on or after the date of lens dispensing or is increasing in severity after dispensing, then the AE will be considered treatment-emergent. Only TEAEs will be summarized in the tables.

The number and percent of eyes with any TEAEs, and the number of subjects with any systemic TEAEs, will be summarized by SOC and PT and by treatment group. At each level of tabulation (e.g., at the PT level), eyes/subjects will be counted only once if they had more than one such event reported during the AE collection period.

The following summary tables will be presented for TEAE data, by SOC and PT:

- TEAEs
- Serious TEAEs
- TEAEs leading to withdrawal from the study
- TEAEs leading to lens wear discontinuation

All TEAEs and non-TEAEs will be presented in a by-subject listing.

ADEs will not be summarized, but will be presented in by-subject listings.

10.2. Deaths, Serious Adverse Events and Other Significant Adverse Events or Adverse Device Events

Any deaths, serious AEs, AEs leading to withdrawal from the study, AEs leading to lens wear discontinuation, and unanticipated ADEs will be presented in by-subject listings with the other AEs and ADEs.

10.3. Other Safety Variables

All safety variables are listed in Section 5.4.

Categorical safety variables will be summarized descriptively using counts and percentages for each treatment group at each visit.

For continuous safety variables, observed values and change from baseline will be summarized descriptively for each parameter (as appropriate) by treatment group at each visit.

For safety endpoints that assess each eye separately, each eye will be treated independently for summarizations.

Graded slit lamp findings will be assessed at each scheduled follow-up visit (1-Week, 1-Month, 2-Month, and 3-Month/Exit Visits) and, optionally, at unscheduled visits. The number and percentage of eyes with findings Grade >2 at any follow-up visit, including unscheduled visits, will be presented by treatment group. Corneal scar findings will not be tabulated but will be listed.

Pinhole VA results for eyes with a 2-line decrease in BCDVA or worse from baseline will be listed with the Distance logMAR VA data.

Lens discontinuation will be assessed at each scheduled follow-up visit (1-Week, 1-Month, 2-Month, and 3-Month/Exit Visits) and, optionally, at unscheduled visits. The time to discontinuation will be based on the study lens exposure weeks defined in Section 8.6. The lens discontinuation rate at each follow-up visit will be presented by treatment group.

The use of unpreserved lubricant eyedrops or artificial tears will be assessed for each follow-up visit by counting the number of drops recorded in the OTC Artificial Tears Log for the period between each visit.

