	
20. History of any corneal surgery (eg, refractive surgery or therapeutic) in either eye
 
21. Any systemic disease currently affecting ocular health or which, in the Investigator's opinion, may have an effect on ocular health in either eye during the course of the study
 
22. Allergy to any component in the study care products
 
23. Meet any of the following criteria:
 
a. Subject is an employee of the investigative siteb. Subject or a member of the subject's household is an ophthalmologist, an optometrist, an optician, or an ophthalmic assistant/technicianc. Subject or a member of the subject's household is an employee of a manufacturer of contact lenses or contact lens care productsd. Subject or a member of the subject's household is an employee of a market research firm
Planned study period and duration of treatment:	The duration of lens wear (and duration of study participation) will be approximately 90 days.
Test lens:	
The Deseyne (vifilcon C) investigational spherical soft hydrophilic lens is proposed to be indicated for the optical correction of refractive ametropia (myopia and hyperopia) in phakic and/or aphakic persons with non-diseased eyes with up to and including 1.00 D of astigmatism that does not interfere with VA.
 
• Sphere power: -12.00 to +7.00 D• Diameter: 14.1 mm• Base curve: 8.6 mm• Material: vifilcon C
Control lens:	
1-Day Acuvue Moist (etafilcon A) daily disposable soft contact lens (Vistakon):
 
• Sphere power: -9.00 to +6.00 D• Diameter: 14.2 mm• Base curve: 8.5, 9.0 mm• Material: etafilcon A

Schedule of study visits:	Visit Number	Visit Name	Target	Acceptable Visit Range
	1	Screening Visit	None	Day -30 to -7
	2	Dispensing Visit	Day 1	Not applicable
	3	1-Week Visit	Day 8	Day 5–9
	4	1-Month Visit	Day 31	Day 27–35
	5	2-Month Visit	Day 61	Day 54–68
	6	3-Month/Exit Visit	Day 92	Day 91–101
Primary effectiveness endpoints:	
There will be 2 primary effectiveness endpoints for the study:
 
 1. Change from baseline to each post-baseline visit in distance logMAR VA by eye 2. Number and percentage of subjects, where there is no more than a 5–logMAR letters read loss from baseline (change from baseline in number of letters read ≥ -5). This is calculated by eye at each post-baseline visit. 			

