4.1.4. Secondary Safety Endpoints

- Adverse events (AEs) and reactions (serious and incidental)
- Adverse device effects (ADEs)
- Conjunctival hyperemia as measured by the Cornea and Contact Lens Research Unit (CCLRU) grading scale
- Keratometry
- Slit lamp biomicroscopy
- Spherocylindrical refraction

- Corneal fluorescein staining
- Best-corrected distance visual acuity (BCDVA)
- Pinhole VA (for eyes with a 2-line decrease in BCDVA or worse from baseline)
- Lens discontinuation rates at any follow-up visit
- Use of unpreserved lubricant eyedrops or artificial tears during the study

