Over-refraction and distance VA		X	X	X	X	X
Lens wettability/centration/movement		X	X	X	X	X
Lens deposits		X	X	X	X	X

PROCEDURE/ASSESSMENTS	Screening Visit 1 Day -30 to -7	Dispensing Visit 2 Day 1	1 Week Visit 3 Day 6-10	1 Month Visit 4 Day 27-35	2 Months Visit 5 Day 54-68	3 Months/Exit Visit 6 Day 91-101 ^a
Without lenses						
Keratometry	X					X
Spherocylindrical refraction	X					X
BCDVA	X					X
Slit lamp exam	X	X	X	X	X	X
Corneal fluorescein staining	X	X	X	X	X	X

BCDVA, best-corrected distance visual acuity; CCLRU, Cornea and Contact Lens Research Unit; HIPAA, Health Insurance Portability and Accountability Act; VA, visual acuity.

a. The 3-Month/Exit Visit MUST occur no earlier than Day 91.

b. Materials to be dispensed at the Dispensing Visit include study lenses and a daily log of eyedrop usage; materials to be returned at the 3-Month/Exit Visit include any unworn lenses (worn lenses do not need to be returned) and the daily log of eyedrop usage.

c. To be performed with lenses in place using an external light source (ie, pen light) and the CCLRU (University of New South Wales, Sydney, Australia) conjunctival hyperemia grading scale (0-3).

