12. APPENDICES

12.1. List of Planned Tables

The list of planned tables includes all of the *main* tables to be presented

Table	Description of Table	All	Safety	ITT	PP
14.1.1.1	Subject Disposition	X			
14.1.2.x	Demographics and Baseline Characteristics		X	X	X
14.1.3.x	Baseline Lens Characteristics		X	X	X
14.1.4.1	Prior Medications		X		
14.1.4.2	Concomitant Medications		X		
14.1.5	Study Device Exposure		X		
14.2.1.x	Distance logMAR Visual Acuity by Visit and Eye			X	X
14.2.2.x	Subjects With No More Than 5 Letters Read Loss From Baseline in Distance logMAR Visual Acuity by Visit and Eye			X	X
14.2.3.x	Symptoms/Complaints and Subjective Assessments by Visit and Eye			X	X
14.2.4.x	Lens Wettability, Centration, and Movement by Visit and Eye			X	X
14.2.5.x	Lens Deposits by Visit and Eye			X	X
14.3.1.1	Treatment-Emergent Adverse Events (TEAE) by System Organ Class and Preferred Term		X		
14.3.1.2	Serious Treatment-Emergent Adverse Events (TEAE) by System Organ Class and Preferred Term		X		
14.3.1.3	Treatment-Emergent Adverse Events (TEAE) Leading to Withdrawal From the Study by System Organ Class and Preferred Term		X		
14.3.1.4	Treatment-Emergent Adverse Events (TEAE) Leading to Lens Wear Discontinuation by System Organ Class and Preferred Term		X		

Table	Description of Table	All	Safety	ITT	PP
14.3.3	Eyes With Slit Lamp Findings Grade >2 at Any Follow-up Visit		X		
14.3.4	Conjunctival Hyperemia by Visit and Eye		X		
14.3.5	Keratometry at Final Visit by Eye		X		
14.3.6	Spherocylindrical Refraction at Final Visit by Eye		X		
14.3.7	Corneal Fluorescein Staining by Visit and Eye		X		
14.3.8	Best-corrected Distance Visual Acuity (BCDVA) at Final Visit by Eye		X		
14.3.9	Lens Discontinuation Rate at Each Follow-up Visit by Eye		X		
14.3.10	Use of Unpreserved Lubricant Eyedrops or Artificial Tears by Visit and Eye		X		

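### Lubricant drop use is summarised as a raw count over periods of 7 to 31 days, so unchanged daily use would appear in Table 14.3.10 as a 4.4-fold rise from the 1-Week to the 3-Month Visit

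*SAP*

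**What the plan says.** SAP section 4.1.4 lists "Use of unpreserved lubricant eyedrops or artificial tears during the study" among the secondary safety endpoints, and the protocol synopsis does the same. The log starts at dispensing: footnote b to SAP Table 1 states "Materials to be dispensed at the Dispensing Visit include study lenses and a daily log of eyedrop usage". Table 1 has the log reviewed at the 1-Week, 1-Month, 2-Month and 3-Month/Exit Visits.

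SAP section 10.3 defines the measure. Use is assessed for each follow-up visit "by counting the number of drops recorded in the OTC Artificial Tears Log for the period between each visit". The general rule in the same section is "For continuous safety variables, observed values and change from baseline will be summarized descriptively", by treatment group at each visit. It supplies no denominator. The planned output is Table 14.3.10, "Use of Unpreserved Lubricant Eyedrops or Artificial Tears by Visit and Eye". By-subject data go to Listing 16.2.14. Neither the SAP nor the protocol synopsis converts the count to a rate or otherwise allows for the length of the period.

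**The concern.** A count over a period measures daily use multiplied by the number of days. The first period in this schedule is about a week and the last about a month, so the two columns of Table 14.3.10 are on different scales. A reader who looks across the visits to see whether the need for drops grows or settles with wear would mostly see the calendar. The apparent change would be wrong in size and could be wrong in direction.

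The protocol synopsis says that all analyses are descriptive. The tables are therefore the result, and no later model will adjust for period length.

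**Working it through.** The documents state no expected count or period length, so there is no figure of theirs to reproduce. The inputs are the target days and windows in the protocol synopsis (schedule of study visits) and the windows in SAP Table 1.

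**Periods at target days.** Period length is the target day minus the previous target day. At a constant rate of r drops per day, the expected count is r × days, so ratios of counts equal ratios of days.

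| Visit | Target day | Days in period | Relative to first | Step from previous visit | Count at 1 drop/day | Count if use halves after Week 1 |
|---|---|---|---|---|---|---|
| 1-Week | 8 | 8 − 1 = 7 | 1.00 | – | 7 | 7 |
| 1-Month | 31 | 31 − 8 = 23 | 3.29 | 23/7 = 3.29 | 23 | 0.5 × 23 = 11.5 |
| 2-Month | 61 | 61 − 31 = 30 | 4.29 | 30/23 = 1.30 | 30 | 0.5 × 30 = 15 |
| 3-Month/Exit | 92 | 92 − 61 = 31 | 4.43 | 31/30 = 1.03 | 31 | 0.5 × 31 = 15.5 |

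The periods sum to 91 days, in line with the stated duration of about 90 days. The apparent rise over the study is 31/7 = 4.43-fold. Most of it is the first step, and the last three periods are fairly similar. For the 3-Month count to fall below the 1-Week count, daily use would have to drop below 7/31 = 23% of its Week 1 level.

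**Spread within a visit.** The shortest period puts the earlier visit on its last allowed day and the later visit on its first. The longest is the reverse. Protocol windows give:

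- 1-Week: 5 − 1 = 4 to 9 − 1 = 8 days (ratio 2.0)
- 1-Month: 27 − 9 = 18 to 35 − 5 = 30 days (ratio 1.7)
- 2-Month: 54 − 35 = 19 to 68 − 27 = 41 days (ratio 2.2)
- 3-Month: 91 − 68 = 23 to 101 − 54 = 47 days (ratio 2.0)

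These are extremes, and typical variation is smaller. For one subject the ratio of last to first period can run from 23/8 = 2.9 to 47/4 = 11.8.

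SAP Table 1 gives the 1-Week window as Day 6–10, where the protocol has Day 5–9. With the SAP window the first period is 5 to 9 days and the ratio runs from 23/9 = 2.6 to 47/5 = 9.4. The two windows should be reconciled, but the finding does not depend on which one holds.

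**Shortened or merged periods.** SAP section 7.3.3 assigns early-termination data to the closest visit, or to the next available one if that visit already has data. Take a subject seen on Day 31 who terminates on Day 40. The closest visit (1-Month) is filled, so the data move to 2-Month. If the rule is applied to the log, 40 − 31 = 9 days of drops sit beside other subjects' 30 days. Conversely, if the 1-Month Visit is missed and the log is next reviewed at 2-Month, one count could cover 61 − 8 = 53 days.

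**After the fix.** At a constant 2 drops per day the raw counts are 14, 46, 60 and 62. Drops per day are 2.0 at all four visits.

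**The case against.** The strongest reply is that the trial compares two lenses, not time points. Both arms follow one schedule and randomization is stratified by site, so at any visit the expected period length is the same in each arm and the 4.4-fold pattern appears equally in both. No analysis of trend in drop use is planned. This stands, and it limits the finding to how the table reads across visits plus avoidable noise within a visit.

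A reader might go further and infer that raw counts bias the comparison in favour of the less well tolerated lens, because its early stoppers have shorter logs. The documents do not support that as a finding. They give one overall dropout rate of about 20%, with no difference by arm. Section 7.3.3 does not mention the drop log, and Table 1 provides for return of the log only at the 3-Month/Exit Visit. Heavier use just before stopping could also offset a shorter log. Such bias is possible, but its size and direction cannot be stated.

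A reader might also take the 4.4-fold figure as a steady climb, or as true of every subject. It is neither: it is mostly one step, and it holds at target days.

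Three further replies carry some weight:

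- The visit names hint that the first period is about a week. They do not give the reader a comparable number.
- A total count is a fair summary of use over a whole study. Section 10.3, however, splits it by visit.
- Calendar days ignore unlogged days and days without lens wear. That bears on the choice of denominator and does not justify having none.

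**Conclusion.** The point holds for the summary across visits. Applied as written, section 10.3 makes constant daily use look like a 4.4-fold rise at target days, 3.3-fold of it between the 1-Week and 1-Month Visits, and makes halved use look like a 2.2-fold rise (15.5/7). This assumes attendance on target days and a complete log. Within the windows an individual's ratio can be lower or much higher.

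The shared schedule does not bias the test-versus-control contrast at a given visit. That contrast could be distorted only if visit timing, missed visits or early stopping differed by arm, since a shortened or merged period would then be counted as a full one. The documents neither show nor exclude this.

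The endpoint is secondary and descriptive, and no success criterion rests on it.

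**What to change.** In SAP section 10.3 and Table 14.3.10, summarise drops per day: drops logged in the period divided by the actual days in the period that the log covers. For subjects who stop, end the period at the last day of study lens wear. Count drops over the same days as the denominator, and state which period a visit day belongs to. After a missed visit, divide by the full span covered, so that a merged period is not read as a single one. Keep the raw counts in Listing 16.2.14. The percentage of subjects using any drops is an optional supplement.

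The rate corrects for period length. It does not correct for who is absent from later visits, so the number contributing at each visit should stay in the table.

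The cost is a sentence or two in the SAP and one derived variable. The log is already daily, section 8.6 already uses the dates of dispensing and last lens wear, and visit dates are needed for the windows in any case. No test and no sample size changes.
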